### **4. Trial design**

The trial is a non-randomized multi-centre phase II study. The primary endpoint is the locoregional control rate defined as clinically or pathologically proven absence of tumor in the vulvar and groin area 12 weeks after the last dosis of radiochemotherapy and after groin dissection in cN1,2 patients. The optimal two-stage design [59] is proposed in order to minimize the sample size if the treatment has low activity defined as poor locoregional control.

### **5. Treatment schedule, expected toxicities, dose modifications**

The general treatment principle is that definitive radiochemotherapy is the main treatment for the locally advanced vulvar disease. Surgery for the primary vulvar tumor will only be performed in case of:

1. progressive disease
2. the presence of histologically proven residual disease 12 weeks after the last course of radiochemotherapy treatment.

Patients will only undergo a groin lymph node dissection when the nodes are pathologically positive, bulky on clinical examination or bulky on imaging studies.

## 5.1 Radiotherapy

*External beam radiotherapy (EBRT) target definition (GTV, CTV, PTV) and organ at risk definition according to ICRU-62.*

### Gross tumor volume (GTV)

The GTV includes:

- $GTV_{PT}$  = primary tumor (based on clinical examination and/or CT/MR).
- $GTV_{LN}$  = cytologically / histologically confirmed pathologic lymph nodes.

### Clinical target volume (CTV)

The clinical target volume (CTV) should include:

- $CTV_{PT}$  =  $GTV_{PT}$  with a minimal safety margin of 1 cm
- $CTV_{LN}$  =  $GTV_{LN}$  with a minimal safety margin of 1 cm
- $CTV_{LD}$  = the lymphatic drainage including the (1) mons veneris, (2) inguinal nodes, (3) femoral nodes and (4) the external and internal iliac nodes (5) fossa obturatoria.

The  $CTV_{LD}$  will be defined on a planning CTscan as

- The corresponding vascular structures (femoral-, inguinal- and iliac vessels) with a margin of 0.5 cm.
- any visible lymph node in this area with a margin of 0.5 cm

Of notice: the inguinal area should extend from the symphysis pubis (medial) to the crista iliaca anterior superior (lateral).

### Planning target volume (PTV)

$PTV_{PT} = CTV_{PT}$  with a minimal safety margin of 1 cm  
 $PTV_{LD} = CTV_{LN} + CTV_{LD}$  with a minimal safety margin of 1 cm

### Organs at risk (OAR)

The OAR are the bladder, the rectum, femoral head, vulvar skin. The outer contour of the OAR will be delineated on a planning CT scan for DVH calculations.

### EBRT treatment planning

A planning CT scan is acquired in supine treatment position with full bladder instruction. Adjacent 5 mm-thick transverse images are collected and transferred to a 3D treatment-planning system.

Following delineation of the GTV, CTV, PTV and OAR, a 3D treatment plan will be calculated with dose specification and homogeneity requirements according to the ICRU-50 report (i.e. the dose delivered to the PTV should be  $\geq 95\%$  and  $\leq 107\%$  of the dose prescribed to the ICRU-point).

All patients are to be treated with megavoltage radiation using photons with or without electrons according to local guidelines.

Any treatment technique satisfying dosimetric requirements for the PTV and the OAR is allowed. The use of bolus is usually needed for superficial parts of the PTV (primary tumor and pathologic groin lymph nodes).

A dose volume histogram should be calculated for the OAR. Volumetric and dosimetric parameters to be correlated with clinical toxicity (CTCAE v.3.0) are:

Target dose:

- The dose delivered to 100%, 95% and 90% of the PTVPT + PTVLD (D100, D95, D90)
- The volume of the PTVPT + PTVLD receiving  $\geq 100\%$ ,  $\geq 95\%$  and  $\geq 90\%$  of the prescribed dose (V100, V95, V90).

OAR:

- The mean dose to the bladder and rectum.
- The dose to 0.1cc, 1cc, 2cc and 5cc of the bladder and rectal wall.
- The maximum dose to the vulvar skin.
- The mean, minimum and maximum dose to the femoral head.

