### Dose and fractionation EBRT

#### General treatment guidelines:

- EBRT will be delivered in a planned overall treatment time of 7 weeks **without a planned treatment break**.
- All PTV's will be treated with fraction doses of 1.8 Gy.
- Treatment will start on Monday with radiation of the PTVPT only.
- Treatment of the PTVLN & LD will start on Wednesday during the second week of treatment.

[figure not shown]
*This treatment setup is chosen in order the finish treatment on the same day as PTVPT to facilitate a good evaluation of the result after 12 weeks in order to avoid variable evaluation time points and subsequent planning for surgery. This is particularly so for patients with cN1/2 groins. In addition, this schedule is also chosen for cN0 groins in order to have similar treatment schedules for the macroscopic tumor with respect to the chemoradiation schedule.*

- At day 8 of treatment patients will receive 2 fractions on 1 day (i.e. PTVPT only and PTVPT together with PTVLN & LD), separated by at least 6 hrs, preferably 8 hrs.
- Capecitabine will be given concomitantly during week 1 & 2, week 4 & 5 of treatment and week 7 of treatment.

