#### Dose guidelines

- The PTVPT will receive a TTD 64.8 Gy.
- The PTVLN & LD will receive a TTD 50.4 Gy.

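### Target-dose parameters for the toxicity correlation are defined on the sum of two target volumes against one unnamed prescribed dose, although the two volumes are prescribed 64.8 and 50.4 Gy

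*Protocol*

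**What the plan says.** All references are to protocol section 5.1.

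- **EBRT treatment planning** introduces a list with "Volumetric and dosimetric parameters to be correlated with clinical toxicity (CTCAE v.3.0) are". Its target-dose part contains D100, D95 and D90, and V100, V95 and V90. All six are defined on the primary-tumour volume plus the lymphatic-drainage volume; for the V values the text begins "The volume of the PTV PT + PTV LD receiving". The V cut-offs are percentages of a prescribed dose, in the singular and not identified.
- The same list then gives separate metrics for bladder, rectum, vulvar skin and femoral head.
- The same subsection also sets a planning requirement: the dose in the target volume must lie between 95% and 107% of the dose prescribed to the ICRU point.
- **Dose guidelines** prescribe two doses: "The PTV PT will receive a TTD 64.8 Gy" and "The PTV LN & LD will receive a TTD 50.4 Gy".
- **Planning target volume (PTV)** uses the plus sign to join volumes: "PTV_{LD} = CTV_{LN} + CTV_{LD". The volume called PTV_LD there and in the parameter list appears as PTV_LN & LD in the dose guidelines.

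**The concern.** A V value is the percentage of a volume that receives at least a given fraction of a reference dose. It needs one volume and one reference. Here the volume is written as a sum of two parts with different prescriptions, and the reference is left open. Centres in a multi-centre trial could take either dose as the reference, or calculate per volume, and report different quantities under one label.

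A D value needs no reference dose. But D95 or D90 of a combined volume is set by its coldest 5% or 10%. When one part is deliberately given a lower dose, that part determines the result.

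At stake is whether these six parameters carry information about the dose to the primary tumour when they are related to toxicity, or mostly describe how large one target is relative to the other.

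**Working it through.** **Step 1. Reproduce the prescribed doses.** Inputs from the general treatment guidelines: "All PTV's will be treated with fraction doses of 1.8 Gy"; "EBRT will be delivered in a planned overall treatment time of 7 weeks"; treatment of the nodal volume "will start on Wednesday during the second week of treatment", which is treatment day 8; and one extra primary-tumour fraction on day 8. Assumption: five treatment days per week.

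- Primary: 7 × 5 + 1 = 36 fractions; 36 × 1.8 = 64.8 Gy.
- Nodal: days 8 to 35 = 28 fractions; 28 × 1.8 = 50.4 Gy.

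Both stated totals reproduce, so two different reference doses are intended.

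**Step 2. Place a conforming plan on each reference.** The 95-107% requirement is applied to each volume's own dose.

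- Nodal range: 0.95 × 50.4 = 47.9 Gy to 1.07 × 50.4 = 53.9 Gy.
- Primary range: 0.95 × 64.8 = 61.6 Gy to 1.07 × 64.8 = 69.3 Gy.
- Ratio of prescriptions: 50.4 / 64.8 = 77.8%.

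*Reference 64.8 Gy.* The nodal range is 47.88/64.8 = 73.9% to 53.93/64.8 = 83.2% of the reference, all below the 90% cut-off. The primary passes V95 and V90 entirely. With no overlap, combined V95 = V90 = the primary's share of the combined volume.

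*Reference 50.4 Gy.* The primary range is 61.56/50.4 = 122% to 69.34/50.4 = 138% of the reference, and the nodal volume meets 95% by construction. Combined V95 = V90 = 100%. The primary would still pass V95 at 47.9 Gy, which is 73.9% of its own prescription.

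**Step 3. Illustrate over a range of volume shares.** The protocol gives no volumes. Assumptions: dose spread evenly over each volume's 95-107% range, no overlap, primary share p from 10% to 70%. The nodal range is 53.928 − 47.88 = 6.048 Gy wide, so:

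- D95 = 47.88 + 6.048 × 0.05/(1 − p)
- D90 = 47.88 + 6.048 × 0.10/(1 − p)
- V100 against 50.4 Gy = p + (1 − p) × (53.928 − 50.4)/6.048 = p + (1 − p) × 0.583

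| Primary share | D95 (Gy) | D90 (Gy) | V95 and V90 vs 64.8 Gy | V95 and V90 vs 50.4 Gy | V100 vs 50.4 Gy |
|---|---|---|---|---|---|
| 10% | 48.2 | 48.6 | 10% | 100% | 62.5% |
| 30% | 48.3 | 48.7 | 30% | 100% | 70.8% |
| 50% | 48.5 | 49.1 | 50% | 100% | 79.2% |
| 70% | 48.9 | 49.9 | 70% | 100% | 87.5% |

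D100 is 47.9 Gy throughout. A simulation under the same assumptions agrees to within 0.1 Gy or 0.1 percentage points.

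**Step 4. Lower the primary dose by 15% and recompute.** The primary range becomes 0.85 × 61.56 = 52.3 Gy to 0.85 × 69.34 = 58.9 Gy.

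- Combined D100, D95 and D90 do not change: all lie in the nodal range below 52.3 Gy.
- V95 and V90 against 50.4 Gy stay at 100%. V100 against 50.4 Gy does not change either, because 52.3 exceeds 50.4.
- V95 against 64.8 Gy falls from p to 0%. V90 falls to (58.94 − 58.32)/(58.94 − 52.33) = 9% of p.
- Calculated per volume, the primary's own V95 falls from 100% to 0% and its D95 from about 61.9 to about 52.6 Gy. The nodal V95 stays at 100%.

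**The case against.** The strongest reply is that the plus sign may simply mean each of the two volumes. The target-volume subsections define no combined PTV, and the dose guidelines attach one dose to each volume, so the prescribed dose could be read as each volume's own. The same list groups bladder and rectum in one item, where separate values per organ are the natural reading. This reading is possible, but it is not stated. The protocol's only other use of the sign in this context joins volumes, and the paired organs are linked by a conjunction instead. So the point stands as an ambiguity whose literal reading gives poor covariates. It is not proof that any centre will calculate it that way.

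It can also be said that the derivation of an exploratory covariate belongs in an SAP or in the CRF instructions. That would hold had the protocol left the definition open; it defines the parameters itself.

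Several stronger inferences are tempting, and the protocol does not support them:

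- *That the toxicity correlation as a whole fails.* The bladder, rectum, skin and femoral-head metrics are defined separately and are unaffected.
- *That underdosing of the vulvar tumour would be invisible, or that these are the only coverage measures.* The 95-107% planning requirement is a separate check on coverage, and V95 against 64.8 Gy does react to underdosing, though mixed with relative volume.
- *That none of the values can be pooled.* D values need no reference dose; only the V values depend on that choice.
- *That the trial's main result is affected.* The dosimetric correlation is not among the objectives or endpoints in section 2 and does not appear in section 8.

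**Conclusion.** The point holds, as a minor one. On the literal combined reading, V95 and V90 are either the primary's share of the volume (reference 64.8 Gy) or about 100% for any conforming plan (reference 50.4 Gy). D95 and D90 are set by the nodal volume once it makes up more than 5% and 10% of the total. The target-dose half of the planned correlation is then largely uninformative, and the V values may not be comparable between centres. The complete response endpoint, the two-stage rule and the sample size do not depend on it.

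The 77.8% ratio and the 74-83% range follow from the protocol's own figures alone. The table also rests on assumed volume shares, an even dose spread and no overlap. Overlap is plausible, since the lymphatic-drainage volume includes the mons veneris and each PTV adds at least 1 cm, so the exact percentages are illustrative.

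**What to change.** In section 5.1, EBRT treatment planning, state that D100/D95/D90 and V100/V95/V90 are reported separately for PTV_PT and for PTV_LD, each relative to the dose that the dose guidelines prescribe for that volume, and that these separate values enter the correlation with toxicity. Use one name for the nodal volume, which is PTV_LD in one place and PTV_LN & LD in another.

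The cost is one sentence and a consistent label. Both volumes must already be delineated for planning, so no additional procedure or patient is needed, and no dose is changed.

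### The only vulvar-skin dose measure listed for correlation with toxicity is the maximum, which the target-dose rule largely confines to about 61.6-69.3 Gy and which says little about how much skin is irradiated

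*Protocol*

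**What the plan says.** All of this is in section 5.1 of the protocol unless noted.

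- **Organs at risk.** Bladder, rectum, femoral head and vulvar skin are named. Their outer contours are drawn on the planning CT for DVH calculation, and a DVH is required for them.
- **Purpose of the list.** It is introduced with "Volumetric and dosimetric parameters to be correlated with clinical toxicity (CTCAE v.3.0) are".
- **What is listed.** Bladder and rectum get a mean dose and doses to 0.1, 1, 2 and 5 cc. The femoral head gets mean, minimum and maximum. Vulvar skin gets one entry: "The maximum dose to the vulvar skin". Coverage measures (D100, D95, D90 and V100, V95, V90) are listed for the primary-tumour and lymph-drainage PTVs together.
- **Prescription.** The primary-tumour PTV "will receive a TTD 64.8 Gy"; the nodal and drainage PTV "will receive a TTD 50.4 Gy".
- **Homogeneity.** PTV dose should lie between 95% and 107% of the ICRU-point prescription.
- **Geometry.** The primary CTV is the tumour plus at least 1 cm, and its PTV adds at least another 1 cm. Bolus is described as usually needed for superficial parts of the PTV, including the primary tumour.
- **Eligibility (section 3.1).** Measurable disease in the vulvar area is required.

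**The concern.** A correlation needs a predictor that differs between patients. The maximum skin dose is tied to a prescription that is the same for everyone. What plausibly differs is how much vulvar skin receives a high dose, because tumour size and position differ. The maximum does not capture that: one small spot of skin inside the target is enough to set it.

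Skin is not a minor site here. Desquamation is the first short-term morbidity named in section 2.2, and section 1.3 gives poor skin tolerance as the reason most earlier studies kept to moderate doses. If the planned correlation for skin comes out weak or null, a reader may conclude that dose and volume do not matter for skin toxicity. The cause could simply be that the predictor hardly moved.

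**Working it through.** **1. Reproduce the prescribed doses.** The inputs are "All PTV's will be treated with fraction doses of 1.8 Gy", "EBRT will be delivered in a planned overall treatment time of 7 weeks" and "At day 8 of treatment patients will receive 2 fractions on 1 day".

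- Primary: 7 weeks × 5 weekdays + 1 extra fraction = 36; 36 × 1.8 = 64.8 Gy.
- Nodal, starting on treatment day 8 (Wednesday of week 2): 35 − 7 = 28; 28 × 1.8 = 50.4 Gy.

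Both agree with the protocol.

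**2. Dose band in the primary-tumour PTV.**

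- Lower: 0.95 × 64.8 = 61.56 Gy.
- Upper: 1.07 × 64.8 = 69.34 Gy.
- Width: 69.34 − 61.56 = 7.78 Gy, or 12% of the prescription.

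**3. From PTV to skin maximum.** The total margin round the tumour is at least 1 + 1 = 2 cm. For the maximum to reach 61.6 Gy in a compliant plan, only one point of vulvar skin need lie inside the PTV. The floor therefore follows once any skin is in the PTV. The ceiling is less firm, because skin outside the PTV is not covered by the 107% rule.

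**4. Spread of the predictor** (assumption: values evenly spread; SD = width/√12).

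- Whole band: 7.78/√12 = 2.24 Gy, about 3.4% of the band's midpoint.
- Only 100-107%, that is 64.8-69.3 Gy: 4.54/√12 = 1.31 Gy.

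The protocol does not say where in the band plans will fall; the second line is a what-if.

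**5. Effect on a correlation (illustration).** The documents give neither a true dose-toxicity correlation nor an unrestricted SD of skin dose. Assume r = 0.3 or 0.5 and an unrestricted SD of 5 to 15 Gy. With u = restricted SD / unrestricted SD, the range-restriction formula is

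r′ = r·u / √(1 − r² + r²u²).

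Example, r = 0.3 and SD 5 Gy: u = 2.24/5 = 0.449, so r′ = 0.135/√(0.91 + 0.018) = 0.14.

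Power is by Fisher's z at the maximum accrual of 68, two-sided 0.05, counting rejections in the correct direction: Φ(atanh(r′)·√65 − 1.96).

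| Assumed r | Power, no restriction | r′, whole band | Power | r′, 100-107% only | Power |
|---|---|---|---|---|---|
| 0.3 | 70% | 0.05-0.14 | 6-21% | 0.03-0.08 | 4-10% |
| 0.5 | 99% | 0.09-0.25 | 10-54% | 0.05-0.15 | 6-23% |

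With 68 patients, the smallest correlation detectable with 80% power is tanh((1.96 + 0.84)/√65) = 0.33. Every restricted value in the table is below it.

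**The case against.** The strongest case on the other side has five parts.

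- **The 95-107% rule governs the PTV, not the skin, and is worded as a target.** This stands. No section sets a range for skin dose, and applying the band to the skin maximum is an inference. Bolus is only usually needed, electrons and any compliant technique are allowed, and skin outside the PTV has no stated ceiling. A reader might infer that the plan fixes the maximum in every patient, so that correlation is impossible. The text does not support that: some spread remains, and the correlation is restricted, not ruled out.
- **Patients can stop early (section 5.5), which widens the range of delivered dose.** True if delivered dose is used. But the list sits under treatment planning and depends on the DVH, so the planned value is the natural reading. Using delivered dose would also pair low dose with severe toxicity in patients who stop because of toxicity, which would distort the correlation.
- **A skin DVH is already required.** This stands. A reader might infer that the extent of irradiated skin goes unrecorded; in fact it can be derived from planned data. It is just not among the listed correlates.
- **PTV coverage measures are also to be correlated.** They are at best a partial proxy. They pool the primary PTV with the drainage PTV, which covers inguinal, femoral, iliac and obturator regions, and they do not isolate vulvar skin.
- **The correlation is exploratory and could be refined in an analysis plan.** It appears in no objective, endpoint or statistical section, which limits the importance of the point. But the protocol does not leave the choice open: it names the measure.

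**Conclusion.** The point holds in a limited form. The single listed skin measure is poorly suited to its stated purpose. Where vulvar skin lies in the primary-tumour PTV, compliant plans largely confine the planned maximum to about 61.6-69.3 Gy, and the maximum says little about the extent of skin irradiated.

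This rests on two assumptions: that some vulvar skin lies in that PTV in nearly all patients, which the eligibility rule and margins make likely but do not state, and that plans meet the homogeneity rule. The band is arithmetic on the protocol's own figures. The shrunken correlations and power values are illustrations on assumed inputs and show direction and rough size only.

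The consequence is confined to an exploratory dose-toxicity analysis. The response endpoint, two-stage design, sample size and estimates of morbidity rates are unaffected. It is a cheap improvement worth making.

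**What to change.** In the organ-at-risk list under EBRT treatment planning, keep the maximum and add, from the vulvar-skin DVH already required:

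- mean dose to the vulvar skin;
- absolute volume of vulvar skin receiving at least 50.4 Gy;
- absolute volume of vulvar skin receiving at least 61.6 Gy (0.95 × 64.8).

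State that these additional measures are the ones used for the correlation with CTCAE skin grade. State also that they are reporting metrics and not dose limits. Both cut-points come from the protocol's own prescriptions, and no dose, constraint or clinical rule changes.

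The cost is a short text change, three more fields on the dosimetry form and one common definition of the skin contour. The last is needed because the protocol asks only for an outer contour and gives no extent or thickness. Mean dose and absolute volume depend on both, so without a shared rule the values would not be comparable between centres.

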### Dose and fractionation EBRT

#### General treatment guidelines:

- EBRT will be delivered in a planned overall treatment time of 7 weeks **without a planned treatment break**.
- All PTV's will be treated with fraction doses of 1.8 Gy.
- Treatment will start on Monday with radiation of the PTVPT only.
- Treatment of the PTVLN & LD will start on Wednesday during the second week of treatment.

[figure not shown]
*This treatment setup is chosen in order the finish treatment on the same day as PTVPT to facilitate a good evaluation of the result after 12 weeks in order to avoid variable evaluation time points and subsequent planning for surgery. This is particularly so for patients with cN1/2 groins. In addition, this schedule is also chosen for cN0 groins in order to have similar treatment schedules for the macroscopic tumor with respect to the chemoradiation schedule.*

- At day 8 of treatment patients will receive 2 fractions on 1 day (i.e. PTVPT only and PTVPT together with PTVLN & LD), separated by at least 6 hrs, preferably 8 hrs.
- Capecitabine will be given concomitantly during week 1 & 2, week 4 & 5 of treatment and week 7 of treatment.

#### Dose guidelines

- The PTVPT will receive a TTD 64.8 Gy.
- The PTVLN & LD will receive a TTD 50.4 Gy.

### Treatment Schedule

### Normal tissue sparing

Customized blocks can be designed to spare the small bowel, the rectum and the caput femoris.

### Verification of external beam radiation treatment

The positioning of the IRP should be verified and adjusted if necessary according to local verification protocols, using local imaging techniques (i.e. megavoltage films or electronic portal imaging) according to the following rules:

1. at at least 3 consecutive days during the first week of treatment.
2. at least weekly thereafter.

## **5.2 Chemotherapy**

Capecitabine will be given orally twice daily at 825 mg/sqm day 1- 14, 22- 35 and 43-49. of radiotherapy (equivalent to a total dose of 1650 mg/sqm/day). Capecitabine should be taken at approximately 12-hours intervals with water within 30 minutes of a meal.

### *5.2.1 Dose modifications*

If a patient experience a grade 2 or 3 toxicity that is considered possibly related to capecitabine treatment or clearly not related solely to radiation, capecitabine treatment will be interrupted. When the toxicity has resolved to grade 0 to 1, treatment will be restarted without dose adjustment. However, in the case of grade 3 nausea/vomiting or diarrhea not resolving to grade 0 to 1 within 2 days of interruption despite symptomatic treatment, capecitabine treatment will be restarted with a 25 % dose reduction. On the recurrence of toxicity at grade 2 or more severe intensity, treatment will be again interrupted until the toxicity has resolved to grade 0 to 1. Treatment will then be restarted with a dose reduction of 25%. All dose modifications and symptomatic treatments should be documented.

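### Section 5.2.1 does not settle whether capecitabine may restart while grade 3 nausea/vomiting or diarrhoea is unresolved, and gives no rule for a first toxicity above grade 3

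*Protocol*

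**What the plan says.** Section 5.2.1 (Dose modifications) sets out three rules in sequence.

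- **First occurrence.** The trigger is worded "If a patient experience a grade 2 or 3 toxicity that is considered possibly related to capecitabine treatment" (or clearly not due to radiation alone), and capecitabine is interrupted. Then: "When the toxicity has resolved to grade 0 to 1, treatment will be restarted without dose adjustment".
- **Exception, introduced by *However*.** It concerns grade 3 nausea/vomiting or diarrhoea "not resolving to grade 0 to 1 within 2 days of interruption despite symptomatic treatment, capecitabine treatment will be restarted", with the dose reduced by 25%.
- **Recurrence.** "On the recurrence of toxicity at grade 2 or more severe intensity, treatment will be again interrupted until the toxicity has resolved" to grade 0–1, after which treatment restarts, again with a 25% reduction.

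The section also asks that all dose modifications be documented. Section 5.5 lists unacceptable toxicity among the reasons for which a patient may leave protocol therapy, without naming a grade. Section 5.4 lists nausea and diarrhoea as short-term effects of the radiotherapy, and vomiting and diarrhoea as effects of the chemotherapy.

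**The concern.** The exception is the one rule that deals with toxicity that is severe and slow to settle, and it is the one that leaves out the resolution condition. A reader who follows its words restarts the drug in a patient whose toxicity has not come down to grade 0–1. A reader who carries the condition over from the sentences on either side keeps the drug on hold.

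The grade ranges raise a second, smaller point. The first-occurrence rule stops at grade 3, while the recurrence rule has no upper limit. The most severe first events therefore fall outside any interruption sentence.

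What is at stake is the safety of individual patients and uniform delivery of capecitabine. Section 1.5 gives the relatively older population as part of the reason for choosing monotherapy with an interruption. The trial is multi-centre (section 4), and treatment-related toxicity is a secondary endpoint (section 2.3). The toxicities in the disputed sentence are ones the protocol itself expects.

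**Working it through.** No sample size, power or error rate is involved, and the plan states no figure to reproduce. The check is a comparison of the three rules in section 5.2.1.

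| Rule | Trigger | Stated condition for restart | Dose at restart |
|---|---|---|---|
| First occurrence | grade 2 or 3 | resolved to grade 0–1 | unchanged |
| Exception | grade 3 nausea/vomiting or diarrhoea, not at grade 0–1 within 2 days of interruption | none stated | reduced by 25% |
| Recurrence | grade 2 or more severe | resolved to grade 0–1 | reduced by 25% |

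**Step 1: restart timing.** Take a patient with a first grade 3 diarrhoea, possibly related to capecitabine, that is still above grade 1 two days after interruption.

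- *Reading A (literal).* The exception's condition is met and its action is restart. Capecitabine resumes at the reduced dose while the toxicity persists.
- *Reading B (dose only).* The general condition still applies. Capecitabine stays on hold until grade 0–1, and slow resolution changes only the dose at which it resumes.

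To show how far apart these are: section 5.2 gives a daily total of 1650 mg/sqm. If the 25% is taken off that full dose, a scheduled dosing day during the unresolved interval delivers 0.75 × 1650 = 1237.5 mg/sqm under reading A and 0 under reading B. This only illustrates the gap between the readings and says nothing about which is right.

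**Step 2: does the text choose?** *However* follows a sentence that sets both a restart condition and a dose, so it can displace either. The recurrence rule ties restart to resolution in explicit sequence: hold until resolved, then restart. The exception has no such wording. Section 5.5 gives a ground for stopping protocol therapy but no grade and no restart rule. The text therefore does not choose.

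**Step 3: grade coverage.** First occurrence covers grades {2, 3}. Recurrence covers {2 and above}, in the words "On the recurrence of toxicity at grade 2 or more severe intensity". The two rules govern different occasions, and grades 2 and 3 lead to interruption under both, so no single event receives opposite instructions. The only difference is an event above grade 3, which is covered on recurrence and unaddressed on first occurrence. Section 5.5 does not clearly fill that gap, because its list is permissive and names no grade.

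**The case against.** The strongest defence is that reading B is the natural one. The sentence before the exception ends on an unchanged dose, and the exception ends on a reduced dose, so the contrast drawn by *However* may concern the dose alone. The paragraph then forms a coherent ladder: same dose after an ordinary first event, reduced dose after slow-resolving grade 3 nausea/vomiting or diarrhoea, and reduced dose after recurrence. The recurrence rule speaks of treatment being interrupted again until resolution, which hints that earlier interruptions were also meant to last that long.

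This has force. A reader might infer from the literal wording that section 5.2.1 flatly contradicts itself on restart. The document does not support that, because a consistent reading exists. What remains is that the consistent reading has to be supplied by the reader: the exception does not state it, and no other section confirms it.

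A reader might also infer that the two grade ranges contradict each other. They do not, since they apply to different occasions, and nothing tells a centre to continue capecitabine after a first event above grade 3. The rule is simply absent.

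Nor should this be read as undermining the response estimate. The trial is single-arm, so differences between centres cannot bias a comparison of arms. Dose modifications must be documented, so variation would be visible, and no effect on the primary analysis has been shown. Weekly review by the radiation and medical oncologists (section 6.2) gives clinical oversight, but it does not tell the two specialists which reading applies.

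**Conclusion.** The point holds as an unresolved ambiguity. On its literal wording, the grade 3 nausea/vomiting or diarrhoea sentence conflicts with the rules before and after it. On a plausible alternative reading it does not, and the protocol leaves the choice open. Centres could make opposite restart decisions for the same toxicity and both be compliant. Separately, a first event above grade 3 has no stated rule, which is an omission.

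The affected group is narrow: patients with grade 3 nausea/vomiting or diarrhoea lasting beyond 2 days of interruption, and patients with a first toxicity above grade 3. Its size cannot be estimated, because section 5.4 gives neither grades nor frequencies for these effects. The conclusion rests on the wording of sections 5.2.1 and 5.5 alone and assumes that no separate instruction to centres settles the matter. It bears on patient safety and consistent treatment delivery and merits correction; nothing shows that sample size, error rates or the primary analysis are affected.

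**What to change.** Reconcile the sentences of section 5.2.1:

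- State explicitly in the grade 3 nausea/vomiting or diarrhoea sentence whether resolution is required before restart, so that it fits the general and recurrence rules or is openly marked as an exception to them.
- Align the grade ranges for first and recurrent events, or explain why they differ, so that a first event above grade 3 has a stated rule.
- If section 5.5 is meant to cover such events, say so in section 5.2.1.

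Which restart condition, grade range or dose applies is a clinical decision for the investigators, and none is proposed here. The cost is one reworded paragraph by amendment, with no added patients or procedures.
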